### 5.1.1 Additional Data Collection for DHS Linkage Study on COVID-19 Pandemic Impact Among UG3 Participants

We will use data collected by the Wisconsin Department of Health Services (DHS) to estimate the rates of COVID-19 infection, testing, hospitalization, and death, fatal and nonfatal drug overdoses, and vaccination against COVID-19, Hepatitis A and Hepatitis B in the UG3 cohort. To achieve our objectives, we propose a retrospective cohort study that will be facilitated by linking data from several DHS registries with UG3 participants. We propose to provide DHS colleagues with identifiable data from 991 of our prior research participants (identifiers: participant name, date of birth, gender, race, ethnicity, previous address, previous phone number, date of participation in our study) to facilitate linkage with several DHS registries. We are seeking approval for the DHS data linkage via a partial waiver of authorization, waiver of consent, and by maintaining a log of the protected health information provided to DHS per standardized disclosure logs (see here: <https://compliance.wisc.edu/wp-content/uploads/sites/102/2019/02/Accounting-for-Disclosures-Log-Research.pdf>). The linkage process is described below:

1. UW will provide a dataset containing a unique study identification number and participant name, date of birth, gender, race, ethnicity, previous address, previous phone number, and date of study participation to colleagues at DHS.

2. DHS will link identifiers with vital records data to identify the date (from study participation date through present day) and cause of any deaths that have occurred among participants of our prior study, from study participation date through present day.
3. DHS will link identifiers with COVID-19 data captured in WEDSS to identify the date of any COVID-19 tests, confirmed or probable infections, and hospitalizations.
4. DHS will link identifiers with WIR to identify the dates of all COVID-19 vaccination doses received and type of vaccine (brand or whether an mRNA/adenovirus vector vaccine).
5. DHS will link identifiers with WIR to identify the dates of all vaccine doses for hepatitis A or B received (including doses received before study participation, if possible).
6. DHS will link identifiers with hospitalization data to identify overdose events involving an emergency department visit or hospitalization.

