## **D. Protection of Incarcerated Individuals**

For Aim 3, our program is a 12-week intensive case-management program. Therefore we want to ensure that participants who become incarcerated have a way to re-engage with the study and intervention once they are released from jail or prison. If it is learned that a research participant is incarcerated at any time in the study, they will be immediately un-enrolled and research activities will be suspended. Participants in the intervention arm may receive contact from the prevention navigator to notify them of this and explain the process. No data will be collected from the participant during this time. Upon release, participants may contact Vivent Health staff to re-enroll in the study. The consent document will be reviewed with the participant at this time to re-assess willingness to participate. Participants can take their assessment after 2.5-5.5 months from baseline or follow up assessment. If the opportunity to take the assessment is no longer available, then we treat it as missing.

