Follow up contacts will be performed with participants in both the intervention and control groups. Vivent Health study staff will perform all follow up contacts with intervention participants. These follow ups include appointment reminders, appointment scheduling, checking in after an important appointment, booster sessions via phone, and discussing test results. These contacts will be made in accordance to the participants' preferred contact method. Contacts with the control group will all be performed by the project manager on the designated study phone to enhance trust with participants who may not want calls from strangers. Calls will be made to remind them to schedule follow up visits. Control participants will be called no more than 3 times between each research visit to eliminate disruption to their daily lives. All social media interactions will occur using a professional Facebook account separate from personal accounts. Facebook's privacy policy will be given to the participant if they choose to contact their PN via Facebook, and they will be reminded that it is not a secure form of communication. PNs will suggest alternative ways to privately discuss treatment and care in detail. All phone calls and text messages performed by Vivent Health staff will be done on a Vivent Health provided work phone, separate from staff's personal information. These phones have secure codes and laptops have two-factor authentication. Phone calls and text messages sent by the UW research team will be performed on a study phone only accessed by one person with a secure code. No names will be stored in the phone.

*DHS Linkage Study on COVID-19 Pandemic Impact Among UG3 Participants.* Given the transient nature of people who inject drugs, re-consenting participants for this data linkage study and analysis would not be feasible, as the proposed analysis will occur at least two years after original recruitment of UG3 participants when contact information is no longer valid. Moreover, the need for this analysis stems from the COVID-19 pandemic emergency, which was not foreseeable at the time of original recruitment. As such, we will carry out the linkage via a waiver of consent and partial waiver of

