**3.2. Potential adverse events (AEs) and Serious adverse events (SAEs).** Unanticipated problems will be reported to the IRB in accordance with posted guidance. SAEs also may constitute unanticipated problems, depending on the nature of the event. In general, SAEs do not require reporting to the IRB unless they also potentially meet the definition of an unanticipated problem.

An unanticipated problem is an event that meets all of the following criteria:

- Reasonably related to the research;
- Unexpected (in terms of nature, severity, or frequency) given the research procedures that are described in the study-related documents, such as the IRB-approved research protocol and informed consent document, and the characteristics of the participant population being studied; AND
- Suggests that the research places subjects or others at a greater risk of harm (including physical, psychological, economic, or social harm) related to the research than was previously known or recognized

Adverse events (AEs) may occur during data collection may include:

- Violation of confidentiality,
- Discomfort due to assessment procedures,
- Embarrassment in disclosing sensitive personal information,
- Disclosure of information about current and/or intended physical harm persons,
- Current and/or intended abuse of children (that would be reported to child welfare agency)
- Dissatisfaction with the assessment procedures or intervention activities.

The population of focus in this research is at high risk for multiple health consequences that are associated with

substance use disorder, which may constitute serious adverse events. These include development of bacterial infections, blood-borne viral infections including HIV and hepatitis, and sexually transmitted infections. This population is also known to have an elevated risk of drug overdose and death from all causes. Because of this, we will only be reporting death as an adverse event.

Adverse events will be solicited from the study participants using a standardized case report form. Study document review will be performed to abstract additional information as necessary. A contact number for the research program manager and PI will be provided to each subject to contact the study in case of an unanticipated serious adverse event (SAE).

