Potential adverse events will be reviewed as to the assigned treatment group and further classified by severity (life-threatening, serious, non-serious) and expected vs. unexpected. Expected and unexpected adverse events will be monitored at each enrolling site and reported to overseeing agencies as required by federal regulations and local requirements.

**3.6. Staff training.** Staff will be required to demonstrate competence with project protocols prior to implementation. Investigators and field staff have or will be required to complete the NIH required CITI web-based ethics training. Interviews will be supervised by the lead project investigators to ensure protocol adherence. Testing staff will be further required to complete training and demonstrate competence with the fingerstick collection of whole blood specimens (i.e., rapid HIV, HCV, and syphilis point-of-care testing methodology) and phlebotomy blood draws prior to study implementation; and complete annual training in blood borne pathogen control ("universal precautions") to ensure adherence to the Occupational Safety and Health Administration Occupational Exposure to Blood borne Pathogen standards. Any new staff who are hired will be required to complete the training package described above, and demonstrate competency with HIV, HCV, and syphilis testing and counseling. Adverse event assessment, recording, reporting, and investigation will be accomplished through staff training, structured/standardized assessments of untoward occurrences/events, and regular monitoring by the study team.

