#### **4.0 Reporting Procedures to NIDA**

**4.1. Procedures and timeline for reporting AEs and SAEs to NIDA.** Reportable adverse events will be submitted to NIDA annually as part of the annual progress report. This report will describe the event, when it occurred, whether the participant was part of the control or intervention arm, and the outcome/resolution. If there were no AEs that year, a statement that no AEs occurred will be included in the progress report or communicated to NIDA in writing.

In this research, all deaths and unanticipated SAEs determined by the PIs to be likely directly related to study participation will be reported to the IRB and NIDA within 24 hours after the PIs are made aware of the incident. The notification will include a brief explanation of the SAE and when it occurred. A written follow up will be sent within 72 hours of the event. The written follow up will include information on the date of the event, what occurred, actions that were taken by the field staff, any planned follow up, whether the participant was part of the intervention or control arm, whether the event appears to be related to the intervention, and whether the participant will continue in the study. Additionally, the IRB will receive an annual report of all SAEs and AEs meeting the criteria listed above.

**4.2. Reporting of IRB actions to NIDA.** After the IRB has reviewed and determined the course of action for reportable SAEs, the PIs will inform NIDA within 24 hours of the course of action.

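### Appendix 1 reports only death as an adverse event but describes no active vital-status check for the Aim 3 cohort, so deaths may be missed, possibly unequally by arm

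*Combined protocol and SAP*

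**What the plan says.** **Reportable event and how it is found.** Appendix 1, section 3.2 notes that this population is at high risk of many serious events and concludes: "Because of this, we will only be reporting death as an adverse event". The next paragraph says how events are found: "Adverse events will be solicited from the study participants using a standardized case report form". It adds "Study document review will be performed to abstract additional information as necessary" and a telephone number given to each subject. The section closes by saying that events are reviewed by assigned group and that "Expected and unexpected adverse events will be monitored at each enrolling site", without giving a method.

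**Onward reporting.** Under Appendix 1, section 4.1, deaths and unanticipated SAEs judged likely to be directly related to participation "will be reported to the IRB and NIDA within 24 hours after the PIs are made aware of the incident". Reportable events go to NIDA each year with the arm identified. If there were none, NIDA is told that none occurred.

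**Contact.** Section 9.0 H: "Control participants will be called no more than 3 times between each research visit to eliminate disruption to their daily lives". Intervention participants have a 12-week intensive programme (section 2.0, Phase 2 objectives) plus reminders, check-ins and telephone booster sessions, for which no cap is stated. For a participant found to be incarcerated, section 9.0 D says "they will be immediately un-enrolled and research activities will be suspended".

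**Death records.** Section 5.1.1 sets up an individual linkage ("DHS will link identifiers with vital records data to identify the date", and the cause, of any death) for 991 UG3 participants. For Aim 3, section 5.4 and Appendix 1, section 1.7(C) name Medicaid, Corrections, laboratory, disease-surveillance and immunization data. In Appendix 2, overdose death is a county-level outcome.

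**The concern.** Section 3.2 narrows reporting to the one event that a participant cannot report. Without an independent check, someone who has died between visits looks the same as someone who has stopped attending. What staff learn by other means depends on how often they are in touch, and that differs by arm.

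Three things are at stake. The count of deaths that goes to the DMC, the IRB and NIDA may be too low. If it is lower in one arm, a by-arm listing would mislead. And because the plan turns an absence of known events into a written statement that none occurred, failure to look could be read as evidence of safety.

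**Working it through.** The plan states no death rate, expected number of deaths or ascertainment rate, so there is no figure to reproduce. The check sets the routes side by side and then illustrates the scale under assumed values.

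**1. Routes by which an Aim 3 death could become known**

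| Route | Where | Could it reveal a death? |
|---|---|---|
| Participant form, subject telephone number | App. 1, 3.2 | Not from the participant who died |
| Study document review | App. 1, 3.2 | Only if something prompts it; contact logs are described under intervention delivery (App. 1, 1.10) |
| Site monitoring; staff becoming aware | App. 1, 3.2 and 4.1 | Possibly; no method is given |
| Medicaid data, up to 2 years | App. 1, 1.7(C) | Possibly; death is not a named outcome and no route into safety reporting is described |
| UG3 vital-records linkage | 5.1.1 | Yes, but only for Aim 3 participants who were also in UG3; overlap not stated |
| Mortality data | App. 2 | County level, so not individuals |

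No row is an active vital-status check of the Aim 3 cohort.

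**2. Contact by arm.** With visits at 0, 3 and 6 months there are two intervals, so a control receives at most 2 × 3 = 6 study calls, plus the visits. The intervention arm has the 12-week programme and uncapped follow-up contacts. Under section 9.0 D, no data are collected from an incarcerated participant, the one contact mentioned is a navigator's notification in the intervention arm, and return after release is at the participant's initiative. One feature runs the other way: intervention participants enrolled from 1 February to 31 March 2023 have assessments only to month 3 (section 5.4).

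**3. Illustration.** From Appendix 1, section 1.6: 270 intervention and 135 control participants. *Assumed:* the same true six-month risk r in both arms, of 0.5% to 2% (1% to 4% a year × 0.5 year), and the shares of deaths found, a_I (intervention) and a_C (control).

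- Deaths seen = n × r × a
- Deaths missed = 270 r (1 − a_I) + 135 r (1 − a_C)
- Apparent risk ratio = a_I / a_C
- Chance of seeing no control death = (1 − r a_C)^135

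| r | a_I / a_C | Seen, intervention | Seen, control | Missed | Apparent ratio | Chance of no control death seen |
|---|---|---|---|---|---|---|
| 0.5% | 100% / 100% | 1.35 | 0.68 | 0 | 1.00 | 51% |
| 0.5% | 90% / 50% | 1.22 | 0.34 | 0.47 | 1.80 | 71% |
| 1% | 100% / 100% | 2.70 | 1.35 | 0 | 1.00 | 26% |
| 1% | 90% / 50% | 2.43 | 0.68 | 0.95 | 1.80 | 51% |
| 2% | 100% / 100% | 5.40 | 2.70 | 0 | 1.00 | 6.5% |
| 2% | 90% / 90% | 4.86 | 2.43 | 0.81 | 1.00 | 8.6% |
| 2% | 90% / 50% | 4.86 | 1.35 | 1.89 | 1.80 | 26% |

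Other assumed pairs give ratios of 0.90/0.70 = 1.29 and 0.80/0.30 = 2.67. Equal under-ascertainment lowers the count but leaves the ratio at 1.

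**4. What complete data could support.** With every death found, a two-sided Fisher exact test at 5% (270 vs 135) has about 0.4% to 12% power against a doubling of risk in the intervention arm, and 6% to 20% against a doubling in controls, for reference risks of 0.5% to 2%. Full ascertainment therefore corrects the count. It does not create a usable test.

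**The case against.** The strongest reply is that the form was never meant to find deaths. Section 3.2 lists events that participants can report, such as discomfort, dissatisfaction and loss of confidentiality, and a form suits those. Deaths would come through staff. Section 3.6 of Appendix 1 also speaks of structured assessment of untoward events and regular team monitoring. Locator forms are completed in both arms, paid monthly contact updates are possible (section 9.0 L), and controls are recruited during regular exchange services, so the call cap is not their only contact with the agency. The lists of external data sources are not worded as exhaustive.

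This stands in part. Asking participants is the main described route, not the only one, and some deaths will come to light. But none of these routes establishes vital status for a participant who stops appearing.

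Several stronger readings are tempting and are not supported:

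- *No contact after incarceration.* Section 9.0 D allows a navigator's notification in the intervention arm and re-enrolment with later assessments in either arm.
- *Death is the only reportable event.* Section 3.2 says so, but its closing paragraph grades events by severity and section 4.1 includes related unanticipated SAEs.
- *The DMC relies on a between-arm comparison of deaths.* By-arm review is mentioned, but no formal mortality comparison or death-based stopping rule is planned, and step 4 shows that such a comparison would have little power.
- *An existing agreement with the state health department could simply be extended.* Sections 9.0 E and H describe agreements still to be made. The UG3 consent waiver rests on lost contact and an unforeseen pandemic, grounds that do not carry over readily to Aim 3.

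**Conclusion.** The point holds as a gap in ascertainment. The plan restricts adverse-event reporting to death, describes solicitation of participants as the main way of finding events, and gives no active vital-status check for Aim 3. With less study contact in controls, and follow-up after incarceration dependent on the participant's return, deaths may be missed, possibly differentially, and a statement that none occurred may be wrong.

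A reader might go further and infer that deaths will be missed, that they will be missed mainly in controls, or that a real excess will be hidden. The documents do not support that: they give neither a mortality nor an ascertainment rate, and staff at control sites may hear of deaths informally. The size is therefore unknown. Every number in steps 3 and 4 rests on assumed risks, and those in step 3 also on assumed ascertainment shares. They show only that expected counts are small enough for one or two missed deaths to alter a by-arm listing.

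**What to change.** In Appendix 1, section 3.2, add individual linkage to Wisconsin vital records for all 405 Aim 3 participants. Do it identically in both arms, and include un-enrolled participants to the extent that consent, IRB approval and an agreement with the state health department allow. Add vital records to the registries in Appendix 1, section 1.7(C), modelled on section 5.1.1. Run the linkage at least once at study end, and before DMC reviews where records are available.

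Report deaths by arm with person-time, descriptively, and distinguish death from loss to follow-up. State that the linkage supplements the 24-hour reporting of known deaths and does not replace it. Reconcile section 3.2 with section 4.1 on whether death is the only reportable event.

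The cost is administrative: protocol wording, a data agreement, and IRB coverage for 405 records. Names and dates of birth are already collected in both arms (section 4.0), and no visits are added. The limits are record lag, which rules the linkage out for immediate reporting, and out-of-state deaths that will not link. The latter include Minnesota residents, whom section 4.0 admits at the Douglas County site, a control site. Because that limit falls on one arm, unlinked participants should be flagged and counted by arm.

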#### **4.0 Reporting Procedures to NIDA**

**4.1. Procedures and timeline for reporting AEs and SAEs to NIDA.** Reportable adverse events will be submitted to NIDA annually as part of the annual progress report. This report will describe the event, when it occurred, whether the participant was part of the control or intervention arm, and the outcome/resolution. If there were no AEs that year, a statement that no AEs occurred will be included in the progress report or communicated to NIDA in writing.

In this research, all deaths and unanticipated SAEs determined by the PIs to be likely directly related to study participation will be reported to the IRB and NIDA within 24 hours after the PIs are made aware of the incident. The notification will include a brief explanation of the SAE and when it occurred. A written follow up will be sent within 72 hours of the event. The written follow up will include information on the date of the event, what occurred, actions that were taken by the field staff, any planned follow up, whether the participant was part of the intervention or control arm, whether the event appears to be related to the intervention, and whether the participant will continue in the study. Additionally, the IRB will receive an annual report of all SAEs and AEs meeting the criteria listed above.

**4.2. Reporting of IRB actions to NIDA.** After the IRB has reviewed and determined the course of action for reportable SAEs, the PIs will inform NIDA within 24 hours of the course of action.

**5.0 Data Safety and Monitoring Board.** A DSMB will be convened for this study in collaboration with the University of Wisconsin Institute for Clinical and Translational Research (UW ICTR). The ICTR Data Monitoring Committee (DMC) meets the requirements for an independent Data and Safety Monitoring Committee or a Data and Safety Monitoring Board. The DMC is available for UW-Madison investigators when a funding agency, the PI, or IRB requires such a committee or board. The committee is comprised of experienced clinical researchers representing a diversity of backgrounds, skills and knowledge. The DMC helps investigators ensure subject safety, research integrity, and compliance with federal regulations and local policies. The DMC also makes recommendations to the PI that could include actions of continuation, modification, suspension, or termination. Prior to submission of the final protocol and IRB application to the UW Health Sciences Institutional Review Board, the PI requested a DMC consultation using the online application form. After an initial consultation with the DMC, there are no conflicts of interest with the current committee. None of the current board members has no financial and/or scientific ties to the outcome of the study. A list of current voting members are provided in the Appendix. The DMC will alert the investigation team if there is change in membership. If a conflict of interest arises, the PIs will inform NIDA within 24 hours of becoming aware of it. That member will abstain from voting or providing input to the study. As the protocol is refined and/or if a serious adverse event occurs, the DMC will work with the PIs and research team to determine whether or not there is a need to meet more than annually. After

each meeting, the DMC will review emerging data, make recommendations about the trial's conduct, including possibly stopping the trial. At the close of each meeting, the DMC will make one of four recommendations: continue as is, continue but with specific modifications; stop temporarily until specific conditions are met; or terminate. The PIs will report DMC activity as part of their annual project progress report to NIDA.

A report on DMC meetings and activities will be sent to NIDA within 30 days of the meeting. The update will include the following: meeting dates (past and upcoming if known), meeting minutes or summary, current board membership, changes in membership (if applicable), information about any new member(s) (if applicable) including statement that new members have no conflict of interest, and specific board recommendations regarding the research project (if any).

**APPENDIX 2.** Proposed outcome measures for Aim 3

Outcome Type	Data Source ‡	Unit of Analysis	Measure for Cost Analysis	Time Period for Analysis*
Addiction treatment accessibility and utilization				
If I wanted to start a medical treatment for opioid or heroin addiction, I could easily get into a methadone program.	Short-term Client-level	ACASI Survey	Change in Likert-scale	T 0 , T 1 , T 2
In the last 3 months, have you gone to a self-help group like Narcotics Anonymous, Alcoholics Anonymous, Celebrate Recovery, or Rational Recovery?	Intermediate Client-level	ACASI Survey	Change in frequency	✓ T 0 , T 1 , T 2
In the past 3 months, have you received outpatient counseling from a provider or program?	Intermediate Client-level	ACASI Survey	Change in frequency	✓ T 0 , T 1 , T 2
In the past 3 months, have you stayed overnight at a residential or inpatient drug treatment facility?	Intermediate Client-level	ACASI Survey	Change in frequency	✓ T 0 , T 1 , T 2
In the past 3 months, have you been in detox?	Intermediate Client-level	ACASI Survey	Change in frequency	✓ T 0 , T 1 , T 2
In the past 3 months, have you stayed overnight at a sober house?	Intermediate Client-level	ACASI Survey	Change in frequency	✓ T 0 , T 1 , T 2
In the past 3 months, have you gotten buprenorphine maintenance medication—like Suboxone or Subutex—from a doctor or program?	Intermediate Client-level	ACASI Survey	Change in frequency	✓ T 0 , T 1 , T 2
In the past 3 months, have you gotten methadone maintenance from a clinic?	Intermediate Client-level	ACASI Survey	Change in frequency	✓ T 0 , T 1 , T 2
In the past 3 months, have you gotten buprenorphine shots – like Sublocade – from a doctor or program?	Intermediate Client-level	ACASI Survey	Change in frequency	✓ T 0 , T 1 , T 2

If I wanted to start medical treatment for opioid or heroin addiction, I could easily get buprenorphine or Suboxone or Subutex.	Short-term Client-level	ACASI survey	Change in Likert-scale	T 0 , T 1 , T 2
If I wanted to start a medical treatment for opioid or heroin addiction, I could easily get into a methadone program	Short-term Client-level	ACASI survey	Change in Likert-scale	T 0 , T 1 , T 2
Any outpatient visit for MAT for opioid use disorder post initiation of CCPH or control	Intermediate Client-level	Medicaid	Change in frequency	✓ T -2 , T 0 , T 2
Prescription fill for methadone, buprenorphine, naltrexone, probuphine post initiation of CCPH or control	Long-term community-level	Medicaid	Change in frequency	✓ T -2 , T 0 , T 2
Treatment for hepatitis C				
Utilization of HCV treatment among participants	Intermediate Client-level	Medicaid	Change in rate of HCV treatment	✓ T 0 , T 1 , T 2
Successful HCV treatment among participants	Long-term Client-level	WEDSS	Change in cure rate of HCV treatment	T -4 , T 0 , T 4
Decrease in prevalence of HCV	Long-term County-level	WEDSS	Change in rate of HCV by county	T -4 , T 0 , T 4
Do you currently have health insurance or health care coverage?	Short-term Client-level	ACASI Survey	Change in rate of health insurance	T 0 , T 1 , T 2
If I ever tested positive for hepatitis C, I'm confident I could get linked to a medical expert and start hepatitis C treatment.	Short-term Client-level	ACASI Survey	Change in Likert-scale	T 0 , T 1 , T 2
Number of appointments made for HCV treatment	Short-term Client Level	CCPH Program data	Change in frequency	T 0 , T 1 , T 2
Prescription fill for DAAs post initiation of CCPH or control	Intermediate Client-level	Medicaid	Change in frequency	✓ T -2 , T 0 , T 2
Lower risk of viral hepatitis				
Uptake of hepatitis A immunization	Long-term County-level	WIR	Change in rate of hepatitis A immunization among 15-39 year olds	T -4 , T 0 , T 4
Uptake of hepatitis B immunization	Long-term County-level	WIR	Change in rate of hepatitis B	T -4 , T 0 , T 4

			immunization among 15-39 year olds	
I am certain that I got all 3 recommended shots for Hepatitis B.	Intermediate Client-level	ACASI survey	Change in Likert-scale	T 0 , T 1 , T 2
Health department referrals for hepatitis A and B immunization	Short-term Client-level	CCPH Program data	Number of referrals	T 0 , T 1 , T 2
Any outpatient visit that includes immunization for hepatitis A or B	Long-term Client-level	Medicaid	Change in frequency	✓ T -2 , T 0 , T 2
Lower risk of HIV				
Have you ever heard of medicine people can take to prevent HIV?	Short-term Client-level	ACASI survey	Change in rate of knowledge of PrEP	T 0 , T 1 , T 2
It's easy for me to get new, clean syringes or needles.	Short-term Client-level	ACASI survey	Change in Likert-scale	T 0 , T 1 , T 2
It's easy for me and my sex partners to get condoms.	Short-term Client-level	ACASI survey	Change in Likert-scale	T 0 , T 1 , T 2
PrEP utilization	Long-term County-level	IQVIA	Change in number of prescriptions for PrEP	T -4 , T 0 , T 4
Safe injection drug use practices	Intermediate Client-level	ACASI survey	Change in rate of safe injection drug use practices	T 0 , T 1 , T 2
Have you had sex without a condom?	Intermediate Client-level	ACASI survey	Change in rate of sex without a condom	T 0 , T 1 , T 2
Were you diagnosed with an STD in the past?	Intermediate Client-level	ACASI survey	Change in rate of STD diagnoses	T 0 , T 1 , T 2
Have you had sex with more than one person in the past 6 months?	Intermediate Client-level	ACASI survey	Change in rate of sex with more than one person	T 0 , T 1 , T 2
Syringe distribution	Intermediate County-level	Lifepoint	Change in rate of syringe distribution	T -2 , T 0 , T 2
HIV prevalence	Long-term County-level	WEDSS	Change in rate of HIV incidence	T -4 , T 0 , T 4
Lower risk of drug overdose				
If I wanted the overdose reversal drug naloxone or Narcan, I could easily get it.	Short-term Client-level	ACASI survey	Change in Likert-scale	T 0 , T 1 , T 2
Narcan distribution	Intermediate County-level	Lifepoint	Change in narcan distribution	T -2 , T 0 , T 2
Overdose hospitalizations	Long-term County-level	Wisconsin Hospital Administration Data	Change in rate of overdose-related hospitalizations	T -4 , T 0 , T 4

Probable opioid overdose	Long-term County-level	Wisconsin Ambulatory Run Data System	Change in rate of overdose-related ambulatory run	T -4 , T 0 , T 4
Overdose death	Long-term County-level	Wisconsin Mortality data	Change in rate of overdose-related death	T -4 , T 0 , T 4
Smoking cessation				
Quit-line encounters	Short-term Community-level	Quit-line database	Change in number of quit-line uses	T -4 , T 0 , T 4
Do you smoke cigarettes?	Intermediate Client-level	ACASI Survey	Change in prevalence	T 0 , T 1 , T 2
On average, how many cigarettes do you smoke a day?	Intermediate Client-level	ACASI Survey	Change in median number of cigarettes	T 0 , T 1 , T 2
Overall smoking prevalence by county	Long-term County-level	BRFSS	Change in prevalence	T -4 , T 0 , T 4
Self-stigma				
How much do you feel ashamed of using drugs?	Intermediate Client-level	ACASI Survey	Change in Likert- scale	T 0 , T 1 , T 2
How much do you feel people avoid you because you use drugs?	Intermediate Client-level	ACASI Survey	Change in Likert- scale	T 0 , T 1 , T 2
How much do you fear you will lose your friends because you use drugs?	Intermediate Client-level	ACASI Survey	Change in Likert- scale	T 0 , T 1 , T 2
How much do you fear family will reject you because you use drugs?	Intermediate Client-level	ACASI Survey	Change in Likert- scale	T 0 , T 1 , T 2
How much do you think other people are uncomfortable being around you because you use drugs?	Intermediate Client-level	ACASI Survey	Change in Likert- scale	T 0 , T 1 , T 2

\*Data sources used to measure the effectiveness of intervention include:

ACASI Survey: the harmonized survey used in the UG3 phase

WEDSS: Wisconsin Electronic Disease Surveillance System

Medicaid: Wisconsin Medicaid Program

IQVIA: Purchased prescriber data

WIR: Wisconsin Immunization registry

Lifepoint: Syringe service program database of needle exchange encounters and narcan distribution

BRFSS: Behavioral Risk Factor Surveillance System

SAMHSA: Database of DATA-Waived Practitioners

\*Time is measured in 3-month intervals based on the intervention assessment phases

T-4 a year prior to the intervention

T-2 6 months prior to the intervention

T0 Start of the intervention

T1 3 month follow up

T2 6 month follow up

T4 12 month after intervention

